9.3.1.3. Sample Size Estimation

Because this is an extension of the OLE study, the sample size of this study will be based on approximately the number of patients who have completed a Parent study (n = 780 patients in total), and who participated in the OLE study (n = 600 patients in total assuming about 20% dropout rate at 6 months from the Parent studies). Assuming the proportion of responders at Week 52 in the OLE study is 60%, it is estimated that approximately 360 patients will be randomized into this study.

With 360 patients, the study will have at least 90% power to detect a difference of 20% or greater between relugolix Group A and placebo Group B for the primary endpoint. The following assumptions are used to determine the sample size for this study:

- 2-sided type I error rate: 0.05
- Randomization: 1:1
- Responder rate for placebo Group B: 40%
- Responder rate for Group A: 60%
- Dropout rate: 20%

9.3.2. Secondary Efficacy Endpoints

The following secondary efficacy endpoints will be assessed during the randomized treatment period or retreatment period:

- Proportion of women who maintain a menstrual blood loss volume of < 80 mL at Week 104 (52 weeks of the randomized treatment period) as measured by the alkaline hematin method;
- Change from Week 52/Baseline to Week 76/Week 104 in menstrual blood volume (during the randomized treatment period);
- Percentage change from Week 52/Baseline to Week 76 / Week 104 (during the randomized treatment period);
- Proportion of patients who responded (menstrual blood loss volume of < 80 mL) to retreatment with relugolix 40 mg and E2/NETA during the retreatment period among placebo patients whose menstrual blood volume had returned to ≥ 80 mL during the 52-week randomized treatment period;

The following secondary endpoints will be assessed at Week 76 and at Week 104 during the randomized treatment period:

- Proportion of women achieving or maintaining amenorrhea;
- Proportion of women whose menses has resumed (among those who were amenorrhoeic at Week 52/Baseline);
- Time to resumption of menses;
- Proportion of women with menstrual blood volume ≥ 80 mL at any time point during the 52-week randomized treatment period;
- Time to resumption of menstrual blood volume $\geq 80 \text{ mL}$;
- Change from Week 52/Baseline in hemoglobin;
- Change from Week 52/Baseline in SF-36 domain and summary component scores;
- Change from Week 52/Baseline in PGA for function and symptoms scores;
- Change from Week 52/Baseline in the WPAI-UF scores;
- Change from Week 52/Baseline in the UFS-QoL Symptom Severity scale and subscales as well as total scores.

9.3.2.1. Secondary Efficacy Endpoint Analyses

During Randomized Treatment Period

For endpoints evaluating the change from Baseline, treatment comparisons will be performed using a mixed model repeated measures approach with treatment, randomization stratification factors, and treatment by visit interaction included as fixed effects and Week 52/Baseline value included as a covariate. The dependent variable (change from Baseline) for each patient at each visit will be calculated based on visit windows specified in the final Statistical Analysis Plan. In addition, descriptive statistics will be provided by treatment group and by visit.

Change from baseline endpoints will be analyzed censoring the values at the time of retreatment with relugolix with E2/NETA. Details will be specified in the SAP.

For endpoints evaluating proportions, treatment comparisons will be performed using a stratified Cochran-Mantel-Haenszel test as appropriate.

Baseline menstrual blood loss is defined as total menstrual blood loss obtained from the Week 52/Baseline visit prior to the date of the first dose of study drug in this Randomized Withdrawal study as assessed by the alkaline hematin method. The menstrual blood loss during the last ontreatment cycle (Week 104) is the total menstrual blood loss during the last month (up to the last 35 days) on-treatment as assessed by the alkaline hematin method.

For time-to-event endpoints (time to achieving or maintaining a menstrual blood loss volume of $<80~\text{mL}\ 24$ weeks after randomization, time to resuming menses, time to resumption of menstrual blood volume $\geq80~\text{mL})$, time-to-event will be defined as weeks from randomization of the Randomized Withdrawal study to first occurrence of the event. Patients without an event will be censored at last assessment date prior to the end of study. Kaplan-Meier methods will be used to describe the time to event distributions for each study treatment arm.

For binary endpoints, the point estimate and 2-sided 95% CI for the proportion will be provided by study treatment group.

During Retreatment Period

For placebo patients whose menstrual blood volume had returned to ≥ 80 mL during the 52-week randomized treatment period and received retreatment:

- the proportion of patients who responded to the retreatment (MBL < 80mL) will be estimated along with corresponding 95% CIs at the end of retreatment period
- mean change and mean % change in menstrual blood volume from retreatment to end of retreatment period.

Details on the endpoint analyses including derivations, handling of missing data, and statistical methods will be provided in the SAP.

9.4. Pharmacodynamic Analyses

Pharmacodynamic estradiol concentration data will be listed and summarized by treatment arm and visit.

9.5. Safety Analyses

Safety assessments will include treatment-emergent adverse events, vital signs, physical examinations, clinical laboratory tests, 12-lead ECGs, and results of measurements of bone mineral density by DXA.

The treatment-emergent period will be defined as the period of time from the first dose date of extension study drug through approximately 30 days after the last dose of study drug, or the date of initiation of another investigational agent or hormonal therapy affecting the hypothalamic-pituitary-gonadal axis or surgical intervention for uterine fibroids, whichever occurs first. Safety will be assessed through summaries of adverse events, the frequency of treatment discontinuations due to adverse events, laboratory evaluations, and bone densitometry results.

The severity of all adverse events is to be evaluated by the investigator based on the National Cancer Institute's CTCAE. All adverse events will be coded to preferred term and system organ class using MedDRA 20.0 or higher. The incidence of adverse events will be presented by MedDRA system organ class and preferred term, relationship to study drug treatment, and severity. A patient reporting the same adverse event more than once is counted once, and at the maximum severity or strongest relationship to study drug treatment when calculating incidence.

Laboratory data consist of chemistry, hematology, and hormonal tests. Only data collected by the central laboratory will be used to do the analyses. The National Cancer Institute CTCAE, will be used to categorize toxicity grade for the laboratory parameters. Shift tables will be provided for each gradable parameter to summarize baseline toxicity grade versus post-baseline toxicity grade. For laboratory parameters that are not gradable by the CTCAE, a shift table based upon the normal range (low, normal, and high) will be provided for each parameter to summarize the study Baseline versus post-baseline results. All data will be listed and summarized by visit. The change from study Baseline to each post-baseline study visit will be presented by study treatment group for each laboratory test.

For vital signs parameters, including temperature, all data will be listed and summarized by visit. The change from study Baseline to each post-baseline study visit will be presented by study treatment group for each parameter.

Clinical laboratory data consist of chemistry, hematology, and hormonal tests. Only data collected by the central laboratory will be used to do the analyses.

The incidence of vasomotor symptoms as assessed through adverse event reporting will be summarized by the study treatment arm.

Bone mineral density data will be collected and analyzed by the central radiology laboratory including bone mineral content (g), bone area (area, cm²), and bone mineral density (g/cm²) each for L1, L2, L3, L4, total hip, and femoral neck, and average bone mineral density of L1-L4 (lumbar spine), Z-score for bone mineral density lumbar spine (L1-L4), total hip, and femoral neck.

All BMD data will be listed and summarized by visit. The change, percent change from study Week 52/Baseline to Weeks 76 and 104 and associated 95% CIs will be presented by the study treatment group for each bone mineral density parameter. The number and percentage of patients meeting a bone mineral density decline of at least 3%, 4%, 5%, 6%, or 7% by body area (lumbar spine, total hip, or femoral neck) will be estimated with 95% CIs by the study treatment group.

Additional analyses will be performed to exam the correlation between bone mineral density loss with demographic and baseline characteristics and with treatment exposure. Details will be provided in the SAP.

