Appendix Table 1 Monitoring^a of Liver Tests for Potential Drug-Induced Liver Injury

Results	Frequency for Repeating Liver (AST, ALT, Bilirubin [Total and Direct]), Alkaline Phosphatase, and INR Tests
If AST or ALT \geq 3 × ULN and total bilirubin $>$ 2 × ULN or INR $>$ 1.5	Every 24 hours until laboratory abnormalities improve
If ALT or AST \geq 3 × ULN and total bilirubin and INR are normal	Every 48 to 72 hours until laboratory abnormalities improve
If the liver test abnormalities improve AND the patient is asymptomatic	Frequency may decrease

Abbreviations: ALT, alanine aminotransferase; AST, aspartate aminotransferase; INR, international normalized ratio; ULN, upper limit of normal

a. Review frequency of monitoring with medical monitor for an individual patient, in case of questions.

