6.5.2.4. Clinical Laboratory Samples

All protocol-required laboratory assessments must be conducted in accordance with the Study Reference Manual and the protocol Schedule of Activities (see Table 1-1). Laboratory requisition forms must be completed, and samples must be clearly labeled with the Patient Identification Number, protocol number, site/center number, and visit date. Details for the preparation and shipment of samples will be provided. Reference ranges for all laboratory tests will be provided to the site by the central laboratory. The samples collected for clinical laboratory tests are listed in Table 6-1.

Table 6-1 Clinical Laboratory Tests

Chemistry	Hematology	Urinalysis
Potassium	White Blood Cell (WBC) Count	Protein
Chloride	WBC Differential	Glucose
Bicarbonate	Red Blood Cell Count	Blood
Blood Urea Nitrogen	Hemoglobin	Urobilinogen
Creatinine	Hematocrit	Bilirubin
Glucose	Mean Corpuscular Volume	Color and Clarity
Calcium	Platelet Count	pH
Phosphate	Red Blood Cell (RBC)	Leucocyte Esterase
Magnesium	morphology	Ketones
Sodium		Nitrite
Albumin		Specific Gravity
Hemoglobin A1c		Urine Microscopy (reflex
Creatine Kinase		testing based on abnormal
Bilirubin Total		urine analysis)
Alanine Aminotransferase	Lipids	Pregnancy
Aspartate Aminotransferase	Total Cholesterol	Pregnancy test
Gamma-Glutamyl Transferase	Low Density Lipoprotein	(human chorionic
Alkaline phosphatase	High Density Lipoprotein	gonadotropin)
	Triglycerides	
Hormones		
Estradiol		
FSH		

The central laboratory will perform laboratory tests for chemistry, hematology, urinallysis, serology, and plasma and serum hormone levels. Each study site will conduct urine pregnancy tests locally.

All laboratory tests with values that are considered abnormal and clinically significant during participation in the study or within 28 days after the last dose of study drug should be repeated until the values return to normal, baseline, or have stabilized. Abnormal and clinically significant results should be reported as adverse events.

The investigator will maintain a copy of the reference ranges (with the record of the reference ranges) for the laboratory or laboratories used.

To maintain blinding, concentrations of hormones will be reported to the investigator, other vendors, and sponsor personnel only after database lock and unblinding.

6.5.2.5. **Electrocardiograms**

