7.5. Adverse Events of Clinical Interest Reporting

Adverse events of clinical interest in this study are defined as any increase in ALT or AST \geq 3 x ULN.

Any ALT or AST elevation of this degree or greater occurring during the open-label Treatment period or Safety Follow-up period should be reported to the sponsor using the Serious Adverse Event Form within 24 hours of the study site personnel's knowledge of the event (see Section 7.6), even if the event does not meet serious adverse event criteria. Additional instructions for evaluating patients with an increase in ALT or AST ≥ 3 x ULN may be found in Appendix 5.

7.5.1. Criteria for Temporary Withholding of Study Drug in Association with Liver Test Abnormalities

Hepatic enzymes will be monitored in accordance with FDA drug-induced liver injury guidelines [FDA, 2009].

If the following liver test abnormalities develop, study drug should be withheld immediately with appropriate clinical follow-up (including repeat laboratory tests, until a patient's laboratory profile has returned to normal/baseline status), and the event reported as a serious adverse event:

- ALT or AST $> 8 \times ULN$; or
- ALT or AST > 5 x ULN and persists for more than 2 weeks; or

- ALT or AST > 3 x ULN and total bilirubin > 2 x ULN or INR > 1.5; or
- ALT or AST > 3 x ULN with appearance of fatigue, nausea, vomiting, right upper quadrant pain or tenderness, fever, rash and/or eosinophilia (> 5%).

Rechallenge may be considered if an alternative cause for the abnormal liver tests (ALT, AST, total bilirubin) is discovered and the laboratory abnormalities resolve to normal or Week 52/Baseline values. The investigator and sponsor must discuss and agree with any decision to rechallenge.

Rechallenge should not occur when the etiology of the liver test abnormalities is considered possibly drug-induced.

7.5.2. Criteria for Permanent Discontinuation of Study Drug in Association with Liver Test Abnormalities

Study drug treatment should be discontinued permanently if all of the following 4 criteria are met (i.e., potential severe drug-induced liver injury/Hy's law case):

- 1. AST or ALT increases to ≥ 3 x ULN; AND
- 2. Total bilirubin increases to $> 2 \times ULN$ or INR > 1.5; AND
- 3. Alkaline phosphatase value does not reach 2 x ULN; AND
- 4. No alternative cause explains the combination of the above laboratory abnormalities; important alternative causes include, but are not limited to the following:

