9.2. Laboratory Data

Laboratory parameters, including chemistry and hematology panels, specified as per protocol for the randomized withdrawal study, and collected from the central laboratory will be tabulated and presented in by-patient listings. Local laboratory parameters will not be used for summary. Urinalysis and hepatitis virus serological test results will be provided in by-patient listing only.

The National Cancer Institute CTCAE Grading Scale with numeric component will be used to categorize toxicity grade for laboratory parameters (CTCAE v5.0, dated 27 Nov 2017). Parameters that have criteria available for both low and high values (eg, hypercalcemia for a high value of calcium and hypocalcemia for a low value of calcium) will be summarized for both criteria (low and high). Patients will only be counted once for each criterion. The same patient can be counted for both criteria if she has laboratory values meeting each criterion. Shift tables will be provided for each parameter, which is gradable by the CTCAE, to summarize Week 52/Baseline toxicity grade versus worst post-Baseline toxicity grade during this randomized withdrawal study. For laboratory parameters that are not gradable by the CTCAE, a shift table based upon the normal range (low, normal, and high) will be provided for each parameter to summarize the Week 52/Baseline versus worst post-Baseline results during this randomized withdrawal study. A shift table for selected parameters based on predefined

categories (refer to [Appendix 1](#)) will be provided to summarize Week 52/Baseline category versus post-baseline category in the randomized withdrawal study. The parameters include glucose, fasting glucose, HbA1c, low density cholesterol, and high-density cholesterol.

Boxplots of laboratory values over time in the randomized withdrawal study, will be plotted for key laboratory parameters. These laboratory parameters include, but are not limited to, hematology (hemoglobin, platelets, leukocytes, neutrophils), creatinine, glomerular filtration rate, and hepatic function panel (alanine aminotransferase [ALT], aspartate aminotransferase [AST], alkaline phosphatase [ALP], and total bilirubin).

The change from Week 52/Baseline to each post-Baseline study visit will be presented by treatment group for each laboratory test in both tables and figures.

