The number and proportion of patients with liver test elevations will be presented by treatment group. Liver test elevations are assessed by using post-Baseline results for ALT, AST, ALP, and total bilirubin based on the definitions presented in [Table 16](#).

Table 16: Categories of Liver Test Elevations

Laboratory Test	Category
ALT or AST	ALT or AST > ULN < 3 × ULN ALT or AST ≥ 3 × to < 5 × ULN ALT or AST ≥ 5 × to < 10 × ULN ALT or AST ≥ 10 to < 20 × ULN ALT or AST ≥ 20 × ULN
Total bilirubin	Total bilirubin > 2 × ULN
ALT or AST and total bilirubin	ALT or AST ≥ 3 × ULN + total bilirubin > 2 × ULN
ALT or AST, total bilirubin, and ALP	ALT or AST ≥ 3 x ULN + total bilirubin > 2 × ULN + ALP < 2 × ULN

Abbreviations: ALP = alkaline phosphatase; ALT = alanine aminotransferase; AST = aspartate aminotransferase; ULN = upper limit of normal.

The number and percentage of patients with concurrent (defined as measurements on the same day) ALT or AST ≥ 3 × ULN and total bilirubin > 2 × ULN will also be presented.

Selected chemistry and hematology test results meeting pre-defined limits of change at any time and based on last observation on treatment will be also summarized per pre-defined threshold (refer to [Appendix 2](#)) by treatment group.

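### The SAP's combined liver-injury row leaves out the protocol's INR alternative, and the central-laboratory-only rule has no liver exception, so the laboratory liver tables can miss cases that meet the protocol's own laboratory criteria

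*Protocol*

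**What the plan says.** **Case definition.** Protocol 7.5.2 requires four things together: ALT or AST at least 3 x ULN; total bilirubin above 2 x ULN "or INR > 1.5; AND" then "Alkaline phosphatase value does not reach 2 x ULN; AND" and finally no alternative cause. The INR alternative also appears in protocol 4.5, 7.5.1 and Appendix Table 1, so it is not a slip.

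**Tabulation.** SAP 9.2 states: "Liver test elevations are assessed by using post-Baseline results for ALT, AST, ALP, and total bilirubin". The last row of Table 16 is "ALT or AST ≥ 3 x ULN + total bilirubin > 2 × ULN + ALP < 2 × ULN". Appendix 2 repeats that combination, and the separate same-day count pairs ALT or AST with bilirubin. INR appears in none of them.

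**Data source.** Protocol 9.5 states: "Only data collected by the central laboratory will be used to do the analyses". SAP 9.2 agrees: "Local laboratory parameters will not be used for summary". Neither makes an exception for liver tests. The by-patient listings in SAP 9.2 are likewise described for central-laboratory parameters.

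**Repeat testing.** For the most serious pattern, Appendix Table 1 requires repeats "Every 24 hours until laboratory abnormalities improve". For isolated transaminase elevation the interval is 48 to 72 hours. INR is among the tests to repeat, but no laboratory is named. Table 6-1, which lists the clinical laboratory tests, does not include INR.

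**The concern.** The liver tables should let a reader see how many women met the laboratory pattern that the protocol itself treats as possible severe drug-induced liver injury. As planned, they recognise one of the two routes to that pattern. They would also ignore a peak measured outside the central laboratory, and such a peak would come from a woman under close follow-up. For a signal this rare, the difference between no case and one case can change how the table is read.

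**Working it through.** No figure in the documents needs reproducing here. The check compares the two definitions and then asks which values can enter the tables.

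**1. Protocol criteria against the SAP row.** Treat each laboratory condition as met or not met:

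- A: ALT or AST at least 3 x ULN
- B: total bilirubin above 2 x ULN
- I: INR above 1.5
- P: ALP below 2 x ULN

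Protocol 7.5.2, laboratory part: A and (B or I) and P. SAP Table 16, last row: A and B and P.

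Of the 2 x 2 x 2 x 2 = 16 patterns, only those with A and P both met can qualify under either rule:

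| B | I | Protocol 7.5.2 | SAP row |
|---|---|---|---|
| yes | yes | met | counted |
| yes | no | met | counted |
| no | yes | **met** | **not counted** |
| no | no | not met | not counted |

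Exactly 1 of the 16 patterns is discordant: transaminases and ALP qualify, INR is above 1.5, and bilirubin is not above 2 x ULN. The ALT/AST, bilirubin and ALP thresholds agree between the documents. This result does not depend on which laboratory measures INR, because no SAP liver category uses INR at all.

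**2. Which values enter the tables.**

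- Unscheduled *central* values are kept. SAP 4.3.7 confines visit windows to by-visit summaries, the liver categories use post-baseline results, and the graded shift tables take the worst post-baseline grade.
- *Local* values are excluded by protocol 9.5 and SAP 9.2. A peak measured locally is replaced by whatever central value lies before or after it.
- Scheduled chemistry panels after baseline fall at Weeks 64, 76 and 104 and at follow-up (protocol Table 1-1). Between Weeks 76 and 104, a span of 104 - 76 = 28 weeks, an elevation can be found only by unscheduled testing. Whether that testing counts depends on where it is run.

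**3. What one case would change.** Planned size: 360 randomized 1:1, so 360 / 2 = 180 per arm. Exact binomial upper bounds:

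- No case: upper = 1 - a^(1/180). With a = 0.025 (two-sided 95%) this is 2.0%; with a = 0.05 (one-sided) it is 1.7%.
- One case (1/180 = 0.6%): solve (1 - p)^180 + 180 p (1 - p)^179 = a. With a = 0.025 this is 3.1%; with a = 0.05 it is 2.6%.

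Like for like, one missed case moves the upper bound from 2.0% to 3.1% (two-sided) or from 1.7% to 2.6% (one-sided). Setting the one-sided 1.7% against the two-sided 3.1% would exaggerate the shift.

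**The case against.** **Local repeats are not established.** This stands. Appendix Table 1 names no laboratory, and protocol 6.4 refers to central safety laboratory assessment at unscheduled visits. The SAP sentence on local parameters does not show that local liver results are expected. A reader might infer that repeat-test peaks will be lost; the documents support only that they would be lost if measured locally.

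**Table 6-1 does not bound central testing.** This also stands. Protocol 6.5.2.4 gives the central laboratory serology as well, which Table 6-1 does not list. The absence of INR there leaves its laboratory unspecified; it does not prove that INR is measured elsewhere. The missing SAP row is unaffected.

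**Other outputs would show the case.** Largely right. Protocol 7.5.1 has transaminases above 3 x ULN with bilirubin above 2 x ULN or INR above 1.5 reported as a serious adverse event, whichever laboratory measured them. If ALT or AST was measured centrally, the woman also enters the ALT/AST rows. The adverse-event-of-clinical-interest tables do not depend on the laboratory either. A reader might infer that cases vanish from the safety report; they do not. These routes, however, sort by coded term or by transaminases alone, so none counts women who meet the 7.5.2 combination. The clinical-interest route also has wording to reconcile: protocol 7.5 ties the 24-hour reporting to an open-label treatment period or follow-up, while Table 7-2 says the treatment period.

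**7.5.2 is a discontinuation rule, not a promised table.** True. The SAP does not label its row as a Hy's law count, and the row also lacks the judgement on alternative causes, so it can over-count as well as under-count. Adding INR is therefore an improvement and not the repair of a broken commitment. Even so, the row reproduces the other laboratory conditions of 7.5.2 at the same thresholds, and readers are likely to take it as that count.

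**Conclusion.** The point holds in a limited form. It is certain from the texts that an INR-only case cannot be counted in the combined row, the same-day count or Appendix 2. It is conditional on where repeats are run that peaks are lost under the central-only rule. Both effects are limited to the laboratory liver tables.

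The number of women affected cannot be derived, because the documents give no liver-event rate, no INR rate and no count of local results. The bounds above only show the weight of one case at 180 per arm; they do not predict that one will occur.

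A reader might also take these tables as the answer on liver safety over up to 104 weeks of treatment. They are not: SAP 9.2 covers results after Week 52/Baseline, so up to 52 weeks plus follow-up.

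The change is worth making because it is cheap and brings the tables into line with the protocol's own laboratory criteria.

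**What to change.** 1. In SAP Table 16 and the Appendix 2 liver rows, keep the bilirubin-only rows and add: `ALT or AST >= 3 x ULN + (total bilirubin > 2 x ULN or INR > 1.5) + ALP < 2 x ULN`. Describe it as the laboratory criteria of protocol 7.5.2 without criterion 4 (no alternative cause). Give the same-day count with the INR alternative as well.
2. For the liver-elevation tables only, take each woman's worst post-baseline value from any laboratory, as a multiple of that laboratory's ULN (INR as measured). Keep central-only data for by-visit means and shift tables. Word the exception in both SAP 9.2 and protocol 9.5.
3. State which laboratory's results for repeat liver tests and INR enter the database.

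**Cost.** Wording in two documents, and entry of local liver and INR results with reference limits for the few women followed under Appendix 5. Between-laboratory variation adds a little noise, which multiples of ULN largely remove. Patient management does not change.
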